10.5 Data and Safety Monitoring

A5361s is a prospective, observational study of participants enrolled into REPRIEVE (A5332) **with or without co-enrollment** into A5333s in which no treatment or intervention is provided. The statisticians will prepare quarterly administrative reports. These reports will include participant REPRIEVE (A5332) and A5361s entry information and will also note protocol execution issues such as participant accrual, participant retention, co-enrollment, and endpoint evaluability.

Details of the aforementioned reports will be described in a **Study Progress, Data, and Safety** Monitoring Plan prepared by SDAC prior to enrollment of the first participant.

10.5.1 Interim Monitoring Guidelines

In accordance with the ACTG SOP for Study Data and Safety Monitoring, the Protocol Team will review study enrollment, conduct and feasibility. Benchmarks for data are as follows:

- Enrollment of 600 study participants will be completed over a period of 2 years from enrollment of the first study participant.
- 90% of expected data are available across time points.

10.6 Analyses

The following sections provide a brief overview of the general analytic approaches for the A5361s primary analysis. A detailed plan that fully delineates all planned statistical analyses, and includes secondary and exploratory objectives, will be in a separate Statistical Analysis Plan (SAP).

10.6.1 Effects of Pitavastatin on Physical Function

Descriptive statistics (median, Q1, Q3, P10, P90, min, max) and graphical presentations of each component of the SPPB, its composite score as well as the prevalence of physical function deficits (SPPB \leq 10) will be examined at REPRIEVE (A5332) entry and over time. A5361s entry evaluations performed after the start of REPRIEVE (A5332) study treatment will be excluded from these summaries.

Analyses of chair rise rate will use linear mixed effects models with time modeled on a continuous scale, where REPRIEVE (A5332) entry is time 0.

The primary parameter of interest will be the difference in the rate of change (slope) between placebo and pitavastatin over time (i.e., the interaction between treatment and time). The primary analysis will include available measured outcomes (including those obtained at REPRIEVE [A5332] entry) in the outcome

vector and will omit the treatment group main effect (intercept) from the model. This approach allows for variable evaluation time and inclusion of data for all participants regardless of their time of entry into A5361s. It takes advantage of the fact that randomized group allocation in REPRIEVE (A5332) means that there is no underlying difference in physical function between treatment groups at REPRIEVE (A5332) entry and will be the most powerful [131]. Further, the analysis will be robust in the event of uneven participant drop-out related to the rate of decline in physical impairment. In the event of non-linear change in outcome over time, we will first assess alternative transformations of the outcomes or time axis. If such transformations are not feasible, modeling will be performed using an arbitrary time effect (i.e., time modeled as a factor on four levels). In this case, the treatment effect of interest for the primary treatment group comparison will be the average difference across post-baseline time points; an interaction of treatment and time will also be assessed and secondary comparisons by year will also be presented. It is noted that the power of the study to detect a comparable effect size is reduced under this alternative modelling framework.

These primary analyses will be extended to evaluate subgroup effects of treatment, namely different treatment effects by race (white vs non-white), sex, baseline CD4 cell count (<350 cell/mm vs. \geq 350 cells/mm), ART duration (categorized as <10 or \geq 10 years), physical function deficits at REPRIEVE (A5332) entry (SPPB \leq 10 vs. $>$ 10), and systemic inflammation (by tertile of IIS) at REPRIEVE (A5332) entry. Sensitivity analyses excluding participants who enrolled into A5361s after REPRIEVE (A5332) entry will also be performed.

Given the expected discretized distribution of the remaining SPPB outcomes (including the overall composite score), longitudinal analyses for these measures as well as the self-reported physical function outcomes from the REAP assessment will use the methods of Wei and Johnson to provide an overall assessment of treatment group differences between the groups over time.

The prevalence of the frailty phenotypes and their components over time and by treatment group will be described. Treatment group differences in the prevalence of the frailty phenotype (non-frail, pre-frail, frail) will be assessed via marginal modeling with a cumulative logit using generalized estimating equations.

10.6.2 Evaluation of the mechanistic pathways through which pitavastatin affects physical function

Distributions of the secondary biomarker outcomes as well as outcomes of fatty muscle infiltration will be described and plotted over time. Pointwise treatment group comparisons will use linear regression adjusted for baseline to provide estimation of the difference in the baseline-adjusted level of the outcomes at each time point. Outcome transformations will be applied as appropriate.

Treatment group comparisons of markers of inflammation and immune activation will be limited to those not described in A5333s. Analyses of fatty infiltration of

muscle will also assess the association of these changes with changes in lipid components and HOMA-IR.

The relationship between markers of inflammation/immune activation, fatty infiltration, and physical function will be assessed via longitudinal modeling of the chair rise rate and expanding each of the appropriate models used to assess treatment group difference including pre- and post-treatment biomarker and fatty infiltration outcomes. The analyses will also examine associations with the following measured covariates/risk factors:

- Demographic and behavioral variables (age, race, sex, menopausal status, BMI, smoking, alcohol use, physical activity by REAP)
- Co-morbid conditions (HBV/HCV, hypertension, diabetes mellitus, chronic kidney disease)
- Use of angiotensin-converting-enzyme inhibitor/angiotensin II receptor blocker (ACE-I/ARB) therapy
- HIV-related variables (CD4 cell count [nadir and current]), HIV RNA, antiretroviral exposure (cumulative and current exposure to ART)
- Muscle symptoms (via the myalgia symptom assessment collected through REPRIEVE [A5332])
- Concomitant medications, specifically, ACE-I/ARB therapy and use of hormonal therapy

Given the assumed temporal associations under study, analyses, including on-treatment measures of biomarkers and fatty muscle infiltration, will only include dependent outcomes assessed from month 24 onward. These analyses will be conducted with and without adjustment for treatment assignment to allow assessment of the degree to which the effects of treatment might be mediated through treatment-associated changes. While further, more formal causal mediation analyses are planned, given the expected statistical developments in the relevant statistical methodology over the next 5 years, these analysis plans will be developed closer to the time of analysis.

11.0 PHARMACOLOGY PLAN

Not applicable.

12.0 DATA COLLECTION AND MONITORING

12.1 Records to Be Kept

Electronic case report form screens (eCRFs) will be made available to sites for data entry. Participants must not be identified by name on any data submitted to the DMC. Participants will be identified by the patient identification number (PID) and study identification number (SID) provided by the ACTG DMC upon registration.

12.2 Role of Data Management

- 12.2.1 Instructions for entering study data on eCRFs will be provided by the ACTG DMC. Each CRS is responsible for keying the data in a timely fashion.
- 12.2.2 It is the responsibility of the ACTG DMC to assure the quality of computerized data for each ACTG study. This role extends from protocol development to generation of the final study databases.

12.3 Clinical Site Monitoring and Record Availability

Monitoring visits may be conducted on-site or remotely. Remote visits may include remote source document verification using methods specified for this purpose by NIAID. Remote monitoring visits may be performed in place of, or in addition to, onsite visits to ensure the safety of study participants and data integrity [132]. The site will make available study documents for site monitors to review utilizing a secure platform that is HIPAA and 21 CFR Part 11 compliant. Potential platform options include: Veeva SiteVault, site-controlled SharePoint or cloud-based portal, direct access to Electronic Medical Record (EMR), and Medidata Rave Imaging Solutions. Other secure platforms that are 21 CFR Part 11 compliant may be utilized, as allowed by the DAIDS Office of Clinical Site Oversight (OCSO).

13.0 PARTICIPANTS

13.1 Institutional Review Board (IRB) Review and Informed Consent

This protocol and the informed consent document ([Appendix I](#)) and any subsequent modifications will be reviewed and approved by the IRB or EC responsible for oversight of the study. A signed consent form will be obtained from the participant (or legal guardian, or person with power of attorney for participants who cannot consent for themselves). The consent form will describe the purpose of the study, the procedures to be followed, and the risks and benefits of participation. A copy of the consent form will be given to the participant, or legal guardian and this fact will be documented in the participant's record.

13.2 Participant Confidentiality

All laboratory specimens, evaluation forms, reports, and other records that leave the site will be identified by coded number only to maintain participant confidentiality. All records will be kept locked. All computer entry and networking programs will be done with coded numbers only. Clinical information will not be released without written permission of the participant, except as necessary for monitoring by the ACTG, IRB/EC, NIA, NIAID, NHLBI, OHRP, **and other US, local, and international regulatory entities** as part of their duties.

13.3 Study Discontinuation

The study may be discontinued at any time by the ACTG, IRB/EC, NIA, NIAID, NHLBI, OHRP, or other government agencies as part of their duties to ensure that research participants are protected.

14.0 PUBLICATION OF RESEARCH FINDINGS

Publication of the results of this study will be governed by ACTG and REPRIEVE policies.

15.0 BIOHAZARD CONTAINMENT

Not Applicable

1 INTRODUCTION

This is the primary statistical analysis plan (SAP) for PREPARE (A5361s), a sub-study of REPRIEVE (A5332). It describes the outcome measures and general analytic approaches proposed for the primary statistical analysis, and provides a forum for discussion and ultimate agreement between study team members. The outline of the report contents, tables and figures, specific coding details and data sources will be developed as a separate Analysis Implementation Plan, a supplement to SAP.

This analysis plan may be updated by the study team as new information becomes available outside of the study, and to modify the list of biomarker outcomes of interest closer to the time of analysis. In addition, the plans to evaluate mechanistic pathways through which pitavastatin affects physical function, including causal mediation analyses, will be developed closer to the time of analysis, given the expected developments in the relevant statistical methodology over the next four years.

Note that this is a team-monitored study. The monitoring reports on the study progress, conduct and data collection to the core study team members are outlined in the Study Monitoring Plan and are not part of this document.

2 GLOSSARY

AT	As-Treated
CM	Clarification Memo
DAG	Directed Acyclic Graph
DASI	Duke Activity Status Index
DMC	Data Management Center at Frontier Science (FSTRF)
HU	Hounsfield Unit
IIS	Inflammatory Index Score
ITT	Intention-To-Treat
LoA	Letter of Amendment
mSPPB	Modified Short Physical Performance Battery
REAP	Rapid Eating and Activity Assessment for Patients
SAP	Statistical Analysis Plan
SDAC	Statistical and Data Analysis Center
SPPB	Short Physical Performance Battery

3 DESIGN OVERVIEW

This section is based on the study protocol Version 1.0, clarification memo (CM) #1 and letter of amendment (LoA) #1.

Design	Prospective, observational study of muscle strength and function among HIV-1 infected adults who are receiving pitavastatin or placebo as part of REPRIEVE (A5332). It is desired that a substantial proportion of study participants will also be enrolled in the Mechanistic Substudy of REPRIEVE (A5333s).
Location	US clinical research sites (CRSs) that are participating in REPRIEVE (A5332) and its mechanistic substudy A5333s.
Brief Rationale	With combination ART, longer life expectancy is changing the demographics of the HIV epidemic. However, even with long-term, effective ART, impairment in physical function and frailty are more common than expected and have been associated with an increased risk of falls, hospitalizations, and mortality. Furthermore, the combination of both HIV infection and impaired physical function is associated with a greater risk of mortality than the presence of HIV infection or impaired function alone; and systemic inflammation in HIV-infection has been shown to have a strong relationship with physical function impairment. Therefore, the aging HIV-infected population is an emerging risk group for the accelerated development of mobility disability, in urgent need for interventions to improve physical function and quality of life, possibly through interventions that attenuate the effects of inflammation and immune activation such as statins.
Sample size	600 participants. The participants will be enrolled from the following pools: 
1) Participants newly enrolling into REPRIEVE and A5333s (prospective enrollment from A5333s): Participants should enroll into REPRIEVE and PREPARE concurrently.2) Participants already enrolled into REPRIEVE and A5333s (retrospective enrollment from A5333s): Participants can enroll into PREPARE within 24 months of their entry into REPRIEVE.3) Participants newly enrolling into REPRIEVE who are not co-enrolling into A5333s (prospective enrollment from REPRIEVE): Participants should enroll into REPRIEVE and PREPARE concurrently.
Duration	Up to 48 months, depending on the time of enrollment relative to REPRIEVE (A5332) entry (follow-up until 48 months from REPRIEVE entry).

Intervention	None in A5361s. Pitavastatin or placebo for pitavastatin will be provided in REPRIEVE (A5332).
Primary Objective	(Numbered as in the study protocol.) 1.2.1 To determine whether pitavastatin can slow or prevent the decline in physical function of adults aging with HIV infection. 1.2.2 To evaluate mechanistic pathways through which pitavastatin affects physical function.
Secondary Objectives	(Numbered as in the study protocol.) 1.3.1 To characterize muscle function and muscle attenuation and their association with clinical characteristics and risk factors (such as age, comorbidities, level of physical activity, inflammation/immune activation, lipids) in virologically suppressed HIV-infected older (>45 years) population at low cardiovascular risk. [Note that this secondary objective is intended for a baseline analysis after completion of enrollment and will be outlined in a separate plan prior to analysis of the baseline data.] 1.3.2 To determine the effects of pitavastatin on muscle fat attenuation over 24 months. 1.3.3 To determine the relationship between changes in inflammation/immune activation and skeletal trunk muscle fat infiltration with change in physical function over 48 months. 1.3.4 To determine the impact of pitavastatin versus placebo on self-reported physical activity or sedentary time. 1.3.5 To assess the impact of muscle symptoms on the effect of pitavastatin versus placebo on physical function. 1.3.6 To determine whether changes in muscle fat attenuation are independent of lipid changes and changes in homeostasis model assessment-estimated insulin resistance (HOMA-IR).
Exploratory Objectives	(Numbered as in the study protocol.) 1.4.1 To determine whether the impact of pitavastatin on physical function or fat infiltration is affected by baseline vitamin D levels. 1.4.2 To determine whether the impact of pitavastatin on physical function or fat infiltration is affected by sex hormones (total and free testosterone) or menopausal status. 1.4.3 To determine the effects of pitavastatin on physical function by subgroup (race, sex, CD4 count, physical activity, baseline physical function, duration of antiretroviral therapy (ART), and inflammation).

4 OUTCOME MEASURES

For each outcome measure, the objectives which it will be used to address, are listed in brackets. Note that an outcome may be used in addressing multiple objectives.

4.1 Primary Outcome Measures

- Physical Function: Chair rise rate quantified annually over 48 months [1.2.1, 1.2.2, 1.3.3, 1.3.5, 1.4.1, 1.4.2, 1.4.3]. Participants are asked to perform 10 chair stands. Chair rise rate will be calculated as the number of chair stands performed divided by the time to perform chair stands. If participant is unable to complete 10 chair rises, 9 seconds will be used for each chair rise not completed (i.e. a total of 90 seconds for those who tried but were unable to complete any).
- Mechanistic Biomarker: Inflammatory Index Score (IIS) calculated as $1/3 \log [IL-6] + 2/3 \log [sTNFR-1]$ at REPRIEVE entry and 12 months. [1.2.2, 1.3.3]
- Mechanistic CT: Paraspinal muscle density (attenuation in Hounsfield units [HU]) at REPRIEVE entry and 24 months. [1.2.2, 1.3.2, 1.3.3, 1.3.6, 1.4.1, 1.4.2]

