Summary of Preliminary Data. Our data from multiple cohort studies have shown the high prevalence of physical function impairments among HIV-infected persons, a more pronounced age-related decline in functional performance measurements among HIV-infected persons compared with HIV-uninfected controls beginning in middle-age, and a clear relationship between decreased physical function and clinical outcomes. We have also demonstrated strong and consistent associations between systemic inflammation and physical function measures in multiple studies, as well as more pronounced fatty infiltration of muscle among HIV-infected men versus HIV-uninfected men, suggesting that these would be potential pathways for interventions. Our data showing increased LBM gains among HIV-infected persons randomized to statin therapy also provide compelling rationale for the PREPARE study.

Study Extension. The final, month 48, follow-up visit of A5361s occurred during the COVID-19 pandemic for many participants. Because a large number of final evaluations could not be conducted, study follow-up has been extended to month 60. Data from these final evaluations are crucial to understanding the longer-term effects of statin therapy on physical function in REPRIEVE (A5332) participants.

We will also collect data on distinct changes in physical function that may have occurred between the month 36 and month 60 visits as a result of the COVID-19 pandemic, either directly through infection with the virus, or indirectly due to changes in physical activity, weight gain, social isolation, or stress.

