6.2 Timing of Evaluations

6.2.1 Entry and Post-Entry Evaluations

For participants newly enrolling into REPRIEVE (A5332) and A5333s: **Enrollment into A5361s should preferably occur on the same day as enrollment into A5332 or A5333s** (within 14 days of the visit is acceptable), and **prior to initiation of randomized treatment in REPRIEVE (A5332)**.

For participants newly enrolling into REPRIEVE (A5332) only: Enrollment into A5361s should occur on the same day as enrollment into A5332 when possible (but must occur within 14 days of enrollment into A5332) and must occur prior to initiation of randomized treatment in REPRIEVE (A5332).

For participants already enrolled into **both** REPRIEVE (A5332) and A5333s: The A5361s entry visit can occur at any REPRIEVE (A5332) or A5333s visit (or \pm 14 days of the visit), up to the month 24 visit. Subsequent visits will follow the remaining schedule in [section 6.1](#).

For all participants: All post-entry visits should be scheduled to coincide with the q12 month regularly scheduled REPRIEVE (A5332) visits but within 14 days of visit is acceptable. Post-entry visits should be scheduled from the REPRIEVE (A5332) entry visit.

Enrollment completed in 2018 under PREPARE (A5361s) Version 1.0. In Version 2.0, an additional visit is added to occur at month 60. If the participant is past their Month 60 visit in the REPRIEVE (A5332) study, the PREPARE (A5361s) Month 60 evaluations can be performed at the next REPRIEVE (A5332) in-person visit. Refer to the A5361s Manual of Procedures (MOPS) for special instructions for participants who are already off-study.

ALTERNATE COMPLETION OF POST-ENTRY EVALUATIONS

- **If a participant can safely be seen for an in-person REPRIEVE (A5332) study visit, the A5361s visit that is due at the same time should also be completed.**

If local guidelines or restrictions prevent the site from completing any of the assessments (or components of the mSPPB or frailty assessments) required at a visit, the reason for the missing assessment should be documented in the source documents and on the corresponding CRF. Complete evaluations as possible, even if full mSPPB and frailty assessments cannot be performed.

- If a participant has an in-person REPRIEVE (A5332) study visit but A5361s assessments could not be completed due to local guidelines or restrictions, the assessments should be completed at the next REPRIEVE (A5332) in-person visit if the restrictions have been canceled by then.

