- If an in-person REPRIEVE (A5332) study visit that coincides with an A5361s visit is delayed or missed, the A5361s visit should be completed whenever the participant is next seen for an in-person REPRIEVE (A5332) visit.

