10.2 Outcome Measures

10.2.1 Primary Outcome Measures

10.2.1.1 Chair rise rate measured annually over **60** months

This primary outcome for the primary physical function objective is a simple transformation of the measured outcome of time to perform 10 chair stands. It is chosen to provide a continuous outcome for participants regardless of their ability to perform 10 chair stands.

It is a well-established measure of lower extremity strength and our previous studies in HIV-infected populations have shown that, among components of the SPPB, this measure is the most likely to show deficits [8,100]. In addition, in middle-age adults from the general population, chair rise rate is a strong independent predictor of mortality [123].

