4.2 Secondary Outcome Measures

4.2.1 *Physical Function and Activity Secondary Outcome Measures*

All physical function outcome measures are assessed annually over 48 months (see Section 5), unless otherwise specified below.

Short Physical Performance Battery (SPPB) Outcome Measures [1.2.1]:

- Composite SPPB score (composite scoring of repeated chair stand, balance, and gait speed) (*Guralnik et al. J Gerontol. 1994 Mar; 49(2):M85-94.*) For gait speed, faster of the two results (minimum) will be used.
- Physical function deficits defined as a composite SPPB score <10.

Modified Short Physical Performance Battery (mSPPB) Outcome Measures [1.2.1]:

- Composite mSPPB score, modified slightly from Simonsick et al (*J Gerontol A Biol Sci Med Sci* (2001) 56 (10): M644-M649). The composite score (ranging from 0 to 3) defined as a sum of the following 3 components.
 - Chair rise rate (stands/second), as above, divided by maximal possible performance to derive a ratio between 0 to 1 (1 chair stand/second shown by previous studies will be used as the maximal possible performance unless suggested otherwise by the data).
 - Total standing balance time, as the sum of time to hold each of 3 stands (semi-tandem, tandem, and one-leg), divided by 90 (the allotted time of 30 seconds per each stand) to derive a ratio between 0 to 1.

- Gait speed (meters/second) divided by the maximal possible performance to derive a ratio between 0 to 1 (2 meters/second shown by previous studies will be used as the maximal possible performance unless suggested otherwise by the data).
- Balance defined as ability to hold one leg stand for 30 seconds and as a ratio as defined above.
- Gait speed (meters/second) evaluated by time to complete a 4-meter walk. Average of the two results will be used.

Frailty Outcome Measures [1.2.1]:

Assessment of frailty is based on presence of the following criteria: (1) weight loss, (2) exhaustion, (3) low physical activity, (4) slow walk, (5) weak grip strength as described by Fried et al (*J Gerontol A Biol Sci Med Sci*. 2001 Mar;56(3):M146-56.). For gait speed and grip strength, average of the results will be used.

- Frailty classified as non-frail (no criteria present), pre-frail (1 – 2 criteria present), and frail (≥ 3 criteria present).
- Number of frailty components present.
- Presence of each frailty component (weight loss, exhaustion, low physical activity, slow walk, weak grip strength).

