6.3 Time Variables

For derivation of time variables, month is defined as 30 calendar days (as in REPRIEVE) and year as 360 calendar days. Similarly, year will be defined as 360 calendar days in estimation of annual rate of change in an outcome measure.

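### The SAP still follows protocol Version 1.0 (48 months): by-visit and Wei-Johnson analyses have no place for month-60 data, and the primary outcome is defined over a different period from the protocol

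*SAP*

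**What the plan says.** **SAP.** Section 3 declares its basis: "This section is based on the study protocol Version 1.0, clarification memo (CM) #1 and letter of amendment (LoA) #1". It sets follow-up at 48 months from REPRIEVE entry. Section 4.1 defines the primary outcome as "Chair rise rate quantified annually over 48 months". For the secondary outcomes, section 4.2.1 says: "All physical function outcome measures are assessed annually over 48 months (see Section 5), unless otherwise specified below". The data-source table in section 5 stops at Year 4. Section 6.4 lists visits at months 12, 24, 36 and 48 and sets by-visit windows of ±60 days. Section 6.3 fixes the calendar: "month is defined as 30 calendar days (as in REPRIEVE) and year as 360 calendar days". Section 8.5.1 sorts secondary evaluations into baseline and those four visits, and exempts only the linear mixed and cumulative-logit models. Section 8.2.1 lets the primary model use all available data regardless of windows. DASI is limited to entry and month 24.

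**Protocol (current).** Section 6.2.1: "In Version 2.0, an additional visit is added to occur at month 60". Section 10.2.1.1: "Chair rise rate measured annually over 60 months". Section 10.2.2.1 also takes the secondary function outcomes to month 60. The reason is in section 2.2: "Because a large number of final evaluations could not be conducted, study follow-up has been extended to month 60". Where a visit is delayed or missed, section 6.2.1 says "the A5361s visit should be completed whenever the participant is next seen for an in-person REPRIEVE (A5332) visit". Section 6.3.4 and Table 10.1-1 supply a Year 5 DASI, taken at REPRIEVE month 96 or study termination.

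**Both documents.** If change is non-linear and transformation fails, the fallback model has time as a factor with four levels (protocol 10.6.1, SAP 8.2.2).

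**The concern.** The protocol extended follow-up to recover information lost at month 48 and calls the final evaluations crucial. The SAP, which protocol 10.6 makes the detailed analysis plan, was not brought into line. There are three consequences.

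1. **Data dropped as written.** By-visit summaries and Wei-Johnson analyses have no place for month-60 data or for late month-48 make-ups.
2. **Primary horizon stated two ways.** The 48-month definition in SAP 3, 4.1 and 4.2.1 sits beside the all-data rules in 8.2.1 and 8.5.1. Stopping at month 48 and using everything give different slope estimates.
3. **Fallback one level short.** Four levels cannot hold five annual post-baseline visits.

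These choices bear on a randomized comparison, so they should not be left open until results are known.

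**Working it through.** **1. Windows.** Visit day = 30 × month, ±60 days.

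| Visit | Target day | Window |
|---|---|---|
| Month 12 | 360 | 300–420 |
| Month 24 | 720 | 660–780 |
| Month 36 | 1080 | 1020–1140 |
| Month 48 | 1440 | 1380–1500 |
| Month 60 | 1800 | none in the SAP |

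Month 60 lies 300 days past the last window. A DASI taken at REPRIEVE month 96 would fall on day 2880.

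**2. The plan's own power figure.** Protocol 10.4.1 gives 85% power for 0.29 and 80% for 0.27 rises/min/year, with ρ = 0.6 and 600 participants (300 per arm). It gives no SD and does not say which visits were assumed. The formula it names solves to σ² = m·S·d² / [2(z₀.₉₇₅ + z₀.₈₅)²(1−ρ)], where S is the sum of squared deviations of visit times. The term (1.960 + 1.036)² is 8.98.

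- Years 0–4, S = 10: σ² = 300·10·0.0841 / (2·8.98·0.4) = 35.1, so SD 5.93.
- Years 0–5, S = 17.5: SD 7.84.

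Either SD gives 79.7% power at 0.27, so the two stated points agree with each other but do not reveal the horizon.

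**3. Wei-Johnson outcomes (dropped as written).** Normal approximation, equal weights, ρ = 0.6 borrowed from chair rise. Relative variance of the average difference over K visits is ρ + (1−ρ)/K.

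- K = 4: 0.70. K = 5: 0.68.
- If half of month-48 visits are missing (assumed), add 1/K²: 0.70 + 1/16 = 0.7625, and 0.68 + 1/25 = 0.72.
- Constant effect: loss 1 − 0.68/0.70 = 3%, or 1 − 0.72/0.7625 = 6%.
- Effect growing linearly (mean time 2.5 against 3.0 years): 1 − (6.25/0.70)/(9/0.68) = 33%, or 1 − (6.25/0.7625)/(9/0.72) = 34%.

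**4. Primary slope, only if capped at month 48.** With a common intercept, no treatment main effect and exchangeable correlation, Var = 2σ²(1−ρ)/(m·Q), where Q = Σt² − ρ(Σt)²/[1+(n−1)ρ].

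| Visits (years) | Q |
|---|---|
| 0–3 | 14 − 0.6·36/2.8 = 6.29 |
| 0–4 | 30 − 0.6·100/3.4 = 12.35 |
| 0–3 and 5 | 39 − 0.6·121/3.4 = 17.65 |
| 0–5 | 55 − 0.6·225/4.0 = 21.25 |

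- Complete visits: loss 1 − 12.35/21.25 = 42% (SE 0.0871 against 0.0664 at SD 5.93).
- Half of month 48 missing (assumed): mean Q is (12.35+6.29)/2 = 9.32 against (21.25+17.65)/2 = 19.45; loss 52%.
- Half of month 60 also missing, independently (assumed): mean Q rises only to (21.25+17.65+12.35+6.29)/4 = 14.38; loss 35%.

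These three percentages do not depend on the SD. If slopes vary between participants, the loss is smaller and does depend on it:

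| Outcome SD | Slope SD (assumed) | Loss, complete visits | Loss, half of month 48 missing |
|---|---|---|---|
| 5.93 | 0.5 | 34% | 45% |
| 5.93 | 1.0 | 22% | 33% |
| 7.84 | 0.5 | 37% | 48% |
| 7.84 | 1.0 | 28% | 39% |

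**5. Fallback.** With baseline in the model, the relative variance of the average post-baseline difference is (1−ρ)/K + ρ − ρ²: 0.34 for four visits and 0.32 for five. The loss is 1 − 0.32/0.34 = 6% for a constant effect and 1 − (6.25/0.34)/(9/0.32) = 35% for a linear one.

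**The case against.** The best reply is that the primary analysis is safe. SAP 8.2.1 is the rule that selects the data, protocol 10.6.1 also takes the available outcomes at variable times, and no sentence truncates follow-up. The 48-month wording then only records the old schedule. This largely stands: using all data is the more natural reading, and under it the primary model loses nothing. What remains is that the SAP's outcome definition contradicts the protocol's, and the SAP does not say which governs.

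Second, the actual loss is confined to by-visit summaries and secondary Wei-Johnson analyses, and is about 3% if the effect is constant. That is correct. However, the protocol's hypothesis is a slowed decline, which implies a difference that grows with time, and there the loss is about a third.

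Third, the missing fractions are assumed, since the protocol says only that many evaluations were lost. That is so, and they serve only to show a range.

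Fourth, DASI is not in the protocol's list of secondary outcomes in 10.2.2. True, but Table 10.1-1 includes it among the outcome measures with a Year 5 value, and the SAP gives it a Wei-Johnson analysis.

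Fifth, the four-level fallback is in both documents and rarely needed. It is leftover wording, and that both the level count is shared and the post-baseline reading is inferred does not make room for a fifth visit.

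Finally, SAP section 1 allows updates. It permits the repair but does not supply the missing horizon or window.

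**Conclusion.** The concern holds. Followed as written, the SAP leaves month-60 and late make-up data out of the by-visit and Wei-Johnson results (composite SPPB, for example, and the REAP activity questions, which protocol 10.6.1 assigns to that method). The information lost is about 3% for a constant effect and 33% for a linearly growing one, or 6% and 34% if half of month-48 visits are missing. These figures assume ρ = 0.6, equal weights and a normal approximation.

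The primary model loses nothing if SAP 8.2.1 governs. If it were capped at month 48, the loss would be 42% with complete visits and 52% with half of month 48 missing. It would be lower if slopes vary between participants or month 60 is itself incomplete. The finding rests on the conflict between the documents; the percentages only show what depends on it.

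**What to change.** Before treatment-group results are seen:

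- Align SAP sections 3, 4.1, 4.2.1, 5, 6.4 and 8.5.1 with protocol Version 2.0 and its 60-month horizon.
- State in SAP 4.1 and 8.2.1 that month-60 and late make-up evaluations enter the primary model at their actual time.
- Add a month-60 visit and a pre-specified rule assigning late make-up evaluations to a visit. A ±60-day window at month 60 would end on day 1860 and could still miss visits that protocol 6.2.1 allows later. Wider, non-overlapping windows with a stated upper limit are one option, with ±60 days as a sensitivity analysis.
- State how the month-60 DASI, taken at REPRIEVE month 96 or termination, is timed and used.
- Change the fallback time factor to five post-baseline levels in both documents.

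The cost is a SAP amendment and one protocol wording change, with no new data collection. Wider windows mix somewhat different follow-up times, which the ±60-day sensitivity analysis would show. The exact width is for the team to choose.
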